ORR by treatment arm will be calculated along with the 2-sided 95% CI using the [Clopper-Pearson](#) method (exact CI for a binomial proportion as computed by default by the FREQ procedure using the EXACT option).

In addition, the frequency (number and percentage) of patients with a confirmed BOR of CR, PR, SD, non-CR/non-PD (applicable only to patients with non-measurable disease at baseline), PD, and NE will be tabulated. Patients with confirmed BOR of NE will be summarized by reason for having NE status. The following reasons will be used:

- No baseline assessment
- No evidence of disease at baseline
- No post-baseline assessments due to death
- No post-baseline assessments due to other reasons
- All post-baseline assessments have overall response NE
- New anti-cancer therapy started before first post-baseline assessment
- SD of insufficient duration (<6 weeks after the date of randomization without further evaluable tumor assessments)
- PD too late (>12 weeks after the date of randomization)

Special and rare cases where BOR is NE due to both SD of insufficient duration and late PD, will be classified as ‘SD too early’ (ie, SD of insufficient duration).

The association of study treatment and OR will be tested by the General Association Statistic of the [Cochran-Mantel-Haenszel test \(CMH\)](#) with the randomization strata taken into account. The null hypothesis of no association in any of the randomization strata is tested

against the alternative, which specifies that there is an association between study treatment and tumor response at least in one randomization stratum. The CMH test will be performed at 1-sided alpha level of 0.025.

The stratified odds ratio in terms of OR will also be estimated along with its 95% CI to compare study treatments. The odds ratio is defined as the odds of OR with experimental treatment divided by the odds of OR with control treatment. The Breslow-Day test will be used to check the homogeneity of the odds ratio across the randomization strata. It tests the null hypothesis that odds ratios in all strata are equal against the alternative hypothesis that at least in one stratum the odds ratio is different.

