In case the null hypothesis of homogeneity of odds ratios across strata is not rejected at the 2-sided alpha level of 0.05, the common odds ratio will be determined using the Mantel-Haenszel estimate (by the FREQ procedure using CMH option in SAS); if the null hypothesis of homogeneity of odds ratio across all strata is rejected, the odds ratio per stratum will be calculated with the corresponding exact CI.

BICR vs Investigator Assessment:

Table 11 outlines the possible BOR outcomes by investigator and BICR.

Table 11. Possible BOR Outcomes for Investigator vs BICR

BOR		BICR Assessment					
		CR	PR	SD	Non-CR/ non-PD	PD	NE
Investigator Assessment	CR	n ₁₁	n ₁₂	n ₁₃	n ₁₄	n ₁₅	n ₁₆
	PR	n ₂₁	n ₂₂	n ₂₃	n ₂₄	n ₂₅	n ₂₆
	SD	n ₃₁	n ₃₂	n ₃₃	n ₃₄	n ₃₅	n ₃₆
	Non-CR/ non-PD	n ₄₁	n ₄₂	n ₄₃	n ₄₄	n ₄₅	n ₄₆
	PD	n ₅₁	n ₅₂	n ₅₃	n ₅₄	n ₅₅	n ₅₆
	NE	n ₆₁	n ₆₂	n ₆₃	n ₆₄	n ₆₅	n ₆₆

$\sum_{i=1}^6(n_{ii})$ is the number of agreements on BOR between BICR and Investigator

$\sum_{i,j=1}^6(n_{ij})$ for $i \neq j$ is the number of disagreements on BOR between BICR and Investigator

$N = \sum_{i,j=1}^6(n_{ij})$

The following measures of concordance will be calculated for each treatment arm:

- Concordance rate for BOR = $\sum_{i=1}^6(n_{ii}) / N$
- Concordance rate for response = $[\sum_{i,j=1}^2(n_{ij}) + \sum_{i,j=3}^6(n_{ij})] / N$

Concordance rates are calculated for each treatment arm and, for each metric, the difference in concordance between the experimental and control arms are used to evaluate potential bias. If the concordance is similar across the treatment arms, then this suggests the absence of evaluation bias favoring a particular treatment arm.

Tumor Shrinkage from Baseline:

Tumor shrinkage will be summarized as the percent change from baseline in target lesions (sum of longest diameter for non-nodal lesion and short axis for nodal lesion) per time point. It will be derived as:

- $((\text{Sum of target lesions at week XX} - \text{sum of target lesions at baseline}) / \text{sum of target lesions at baseline}) \times 100$

The maximum reduction in target lesions from baseline will be derived across all the post-baseline assessments until documented disease progression, excluding assessments after start of subsequent anti-cancer therapy, as:

- Minimum of $((\text{sum of target lesions at week XX} - \text{sum of target lesions at baseline}) / \text{sum of target lesions at baseline}) \times 100$

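### The SAP makes the pooled odds ratio for objective response depend on a Breslow-Day test; it should be reported in all cases, with the test as description

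*SAP*

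**What the plan says.** SAP 6.2.2.3 states, with no condition attached: "The stratified odds ratio in terms of OR will also be estimated along with its 95% CI to compare study treatments". It then adds a check: "The Breslow-Day test will be used to check the homogeneity of the odds ratio across the randomization strata". The next paragraph turns the check into a switch: "In case the null hypothesis of homogeneity of odds ratios across strata is not rejected at the 2-sided alpha level of 0.05", then "the common odds ratio will be determined using the Mantel-Haenszel estimate". If homogeneity "is rejected, the odds ratio per stratum will be calculated with the corresponding exact CI". No pooled estimate is named in that second branch.

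Two overall results in the same section do not pass through the switch: the response rate per arm with a Clopper-Pearson interval, and the stratified association test ("The CMH test will be performed at 1-sided alpha level of 0.025").

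SAP 6.2.2 has tumor endpoints analysed by BICR and by investigator, separately in each co-primary population. SAP 6.4 separately plans subgroup odds ratios for response, by BICR, in a forest plot. The two stratification factors are among the subgroups.

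**The concern.** Two statements about the same estimate do not agree: one promises a stratified odds ratio outright, the other plans a pooled value only if a preliminary test is non-significant. Read in sequence, a rejection leaves the trial with four stratum odds ratios and no overall odds ratio or confidence interval for response.

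That makes the reported effect measure depend on the data. The Mantel-Haenszel odds ratio is a usable stratum-weighted summary whichever way Breslow-Day falls, so withholding it gains nothing. The selector is also poor: responses may be few in patients who have just completed chemotherapy, and a test for differing odds ratios over four sparse tables has limited power. What is at stake is the pooled effect estimate and its interval for a secondary endpoint.

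**Working it through.** The plan gives no response-rate assumption, no stratum sizes and no power for Breslow-Day, so it offers no figure of its own to reproduce.

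**Inputs from the documents**
- 668 patients randomized 1:1 (SAP 5.1.1); at least 334 PD-L1-positive (SAP 2.2).
- Two binary stratification factors (SAP 3.4.2), so 2 × 2 = 4 strata and a chi-square test on 3 degrees of freedom.
- Significance level 0.05 (SAP 6.2.2.3).
- Two assessors × two populations = 4 analyses (SAP 6.2.2).

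**Assumptions**
- Control response rate 7.8%. This is the placebo rate in the lapatinib maintenance trial described in protocol 1.2.3.1, borrowed only as an anchor.
- Equal strata: 668/8 = 83.5 per arm per stratum, or 334/8 = 41.75. Expected control responders per stratum are then 0.078 × 83.5 = 6.5 and 0.078 × 41.75 = 3.3.

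**Pooled estimate withheld when the strata truly agree.** With a common odds ratio of 1.9 (the 13.8% vs 7.8% of that same trial gives (0.138/0.862)/(0.078/0.922) = 1.89), simulated Breslow-Day rejection is 3.9-4.7% per analysis over equal and unequal strata. The nominal rate is 5%. If the four analyses were independent, the chance of losing at least one pooled estimate would be 1 − 0.95⁴ = 18.5%. They share patients, so this is only a rough ceiling.

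**How often the test misses a real difference.** The odds ratio differs between the two levels of one factor; control rate 7.8%, equal strata, 20,000 simulated trials per cell:

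| Odds ratios at the two levels | Missed, N = 668 | Missed, N = 334 |
|---|---|---|
| 1.25 and 2.5 (2-fold) | 82.6% | 89.2% |
| 1.1 and 3.3 (3-fold) | 59.4% | 78.0% |
| 0.95 and 3.8 (4-fold) | 40.3% | 66.6% |

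Unequal strata (70/30 or 80/20 on one factor) raise the 4-fold figures to 46-56% and 72-79%. Letting the control rate run from 2% to 20% over the same stratum splits, 2- to 4-fold differences are missed in 9.2% to 98.5% of trials.

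The complement is the chance of losing the pooled value when strata do differ. For the 4-fold case it is 100 − 40.3 = 59.7% at 668 patients and 100 − 66.6 = 33.4% at 334.

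**What replaces it.** As an illustration, take 12/84 vs 7/84 responders in every stratum.
- Each stratum's odds ratio is (12 × 77)/(72 × 7) = 924/504 = 1.83, and the pooled value is the same.
- Pooled 95% CI, with standard error of the log odds ratio 0.252: 1.83 × exp(±1.96 × 0.252) = 1.12 to 3.00.
- Exact 95% CI for a single stratum: 0.62 to 5.80.

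These tables would not themselves trigger rejection. They show only how much precision goes when stratum values stand alone.

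**The case against.** The case for leaving the text alone is that the rule is fully specified and leaves no analyst discretion. No decision hangs on it. Protocol 9.3.2 asks only for response rates per arm with exact intervals, so nothing the protocol promises is lost. The CMH test is ungated, and response lies outside the alpha split for overall survival. The SAP also never says in words that the pooled value is omitted after rejection, and the earlier sentence promises it. All of this stands, and it limits the point to wording and reporting.

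Three stronger readings are tempting and should not be drawn.

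- **That the SAP treats non-significance as proof of equal odds ratios.** It says only which estimate to compute, so this would be an inference.
- **That after non-rejection an effect confined to one chemotherapy-response group would be shown as common to all, with no stratum results.** SAP 6.4 plans the BICR odds ratios by chemotherapy response and by metastatic site whatever Breslow-Day shows. They are by single factor, not by the four crossed strata, and by BICR only, but they are there.
- **That the miss rate is itself the harm.** It rests on response rates, stratum sizes and odds-ratio patterns that the documents do not give. Reporting the Mantel-Haenszel value after a missed difference is not an error, and the change proposed here leaves the miss rate as it is. The miss rate shows only that the test is a weak basis for choosing an estimate.

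What the objection does not answer is the mismatch between the two statements, and the absence of any planned overall odds ratio after rejection.

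**Conclusion.** The point holds as a cheap improvement. SAP 6.2.2.3 makes the pooled odds ratio conditional on a test of limited power, in conflict with its own unconditional statement. That the pooled value is dropped after rejection is the natural reading of the rule, not an explicit instruction.

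The firmest figure is the loss under true homogeneity, about 4-5% per analysis, because it follows mainly from the 0.05 level. Across the four analyses, one population or assessor could end with a common odds ratio and another without, which would prevent direct comparison. The figures for missed or detected differences depend on the stated assumptions and should be quoted only with them. Neither the test of response nor the survival conclusion is affected.

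**What to change.** Replace the conditional rule in SAP 6.2.2.3 with wording such as: *The Mantel-Haenszel common odds ratio, stratified by the randomization strata, will be reported with its 95% CI in all cases. Odds ratios for each stratum with exact CIs, and the Breslow-Day p-value, will be shown alongside as descriptive information.* Apply it to both populations and both assessors.

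The cost is a wording change and a few table rows from quantities the SAP already plans to compute in one branch or the other. The downside is that a pooled value appears even when the strata differ; the stratum values next to it let the reader see that.

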2.2. Study Design

This is a Phase 3, multicenter, multinational, randomized, open-label, parallel-arm efficacy and safety study of avelumab plus BSC compared to BSC alone as a maintenance treatment after completion of first-line platinum-based chemotherapy (gemcitabine + cisplatin or gemcitabine + carboplatin) without evidence of disease progression in adult patients with unresectable locally advanced or metastatic UC.

The study design is illustrated in [Figure 1](#).

Figure 1. Study Design Schema

- a. Allowed first-line chemotherapy regimens are gemcitabine + cisplatin or gemcitabine + carboplatin.
b. Randomization must occur at least 4 and not more than 10 weeks after the last dose of first-line chemotherapy and will be stratified by: best response on 1st-line therapy (CR or PR vs. SD) and metastatic disease site (visceral vs. non-visceral).

CR = complete response; IV = intravenous; PD = progressive disease; PR = partial response; Q2W = every 2 weeks; SD = stable disease

- A total of approximately 668 patients without progressive disease (PD) as per RECIST v1.1 guidelines (ie, with ongoing CR, PR, or SD) after 1st line chemotherapy will be randomized in this study. It is estimated that at least 334 patients with confirmed PD-L1-positive tumors (including infiltrating immune cells) will be randomized in this study.
- Patients will be randomized in a 1:1 ratio into two study arms: avelumab + BSC (Arm A) or BSC alone (Arm B).
- Randomization will be stratified by (i) best response to first-line chemotherapy (CR/PR vs. SD), and (ii) metastatic disease site (visceral vs. non-visceral) at the time of initiating first-line chemotherapy.
- This study is designed with two co-primary populations: 1) patients determined to have PD-L1-positive tumors (including infiltrating immune cells) by a verified GMP PD-L1 IHC test, and 2) all randomized patients.
- Patients must have received at least 4 cycles, but not more than 6 cycles, of a first-line chemotherapy regimen consisting of either gemcitabine + cisplatin or gemcitabine + carboplatin before randomization into this study. No other chemotherapy regimen is allowed as the first line chemotherapy for inclusion in this clinical trial (please see Section 4.1 of the protocol, Inclusion Criteria 2).

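### Similar investigator–BICR concordance across arms cannot show that response assessment was unbiased, because both concordance rates ignore the direction of disagreement

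*SAP*

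**What the plan says.** The trial is a "randomized, open-label, parallel-arm efficacy and safety study of avelumab plus BSC compared to BSC alone" (SAP section 2.2), so investigators know the treatment when they read scans. Objective response by BICR and by investigator is a secondary endpoint (SAP section 3.2.2).

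SAP section 6.2.2.3 cross-tabulates BOR in Table 11. Rows are the investigator and columns are BICR, each in the order CR, PR, SD, non-CR/non-PD, PD, NE. Two rates are calculated per arm:

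- BOR concordance: the sum of the six diagonal cells divided by N.
- Response concordance: patients whom both readers call responders plus patients whom both call non-responders, divided by N.

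The SAP then says that "the difference in concordance between the experimental and control arms are used to evaluate potential bias", and interprets the result as follows: "If the concordance is similar across the treatment arms, then this suggests the absence of evaluation bias favoring a particular treatment arm". It gives no threshold for similarity and no measure of direction.

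For PFS, section 6.2.2.1 has a similar sentence, but there the metrics include the early and late discrepancy rates (EDR and LDR). The SAP also says which sign of each between-arm difference may point to bias in favour of the experimental arm.

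**The concern.** Bias that favours an arm has a direction. For response it means that investigators call responses too readily in Arm A, or too reluctantly in Arm B, relative to BICR. Neither rate carries that information. Moving one patient from agreement to an upgrade (investigator CR or PR, BICR neither) or to a downgrade (BICR CR or PR, investigator neither) lowers either rate by exactly 1/N. Equal rates show that the arms have equal amounts of disagreement. They do not show that the disagreement points the same way.

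At stake is the credibility of investigator-assessed response in an open-label trial. The concordance comparison is the only bias check that the SAP names for response. Read as written, it could lead the report to state that there is no sign of bias when the investigator response rates are shifted in favour of one arm.

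**Working it through.** The SAP gives no concordance figure, so there is none to reproduce. The check applies its two formulas to constructed tables.

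**Inputs.** From SAP section 2.2: about 668 patients randomized 1:1, so 668/2 = 334 per arm. Assumed, because the documents give no values: BICR BOR in both arms of CR 10, PR 24, SD 150, non-CR/non-PD 20, PD 100, NE 30. That makes 34 BICR responders (34/334 = 10.2%) and 300 non-responders per arm, with no true treatment effect on response. All disagreements are placed between PR and SD, so the two concordance rates coincide.

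**Formulas, per arm.** With U upgrades and D downgrades:

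- concordance = (334 − U − D)/334
- investigator ORR = (34 + U − D)/334

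| Case | Arm A U/D | Arm B U/D | Concordance A vs B | Investigator ORR A vs B | Odds ratio |
|---|---|---|---|---|---|
| 1 | 20/0 | 10/10 | 94.0% vs 94.0% | 16.2% vs 10.2% | 1.70 |
| 2 | 20/0 | 0/20 | 94.0% vs 94.0% | 16.2% vs 4.2% | 4.41 |
| 3 | 20/0 | 0/0 | 94.0% vs 100% | 16.2% vs 10.2% | 1.70 |
| 4 | 30/10 | 10/10 | 88.0% vs 94.0% | 16.2% vs 10.2% | 1.70 |

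Case 1 in full: Arm A concordance is (334 − 20 − 0)/334 = 314/334 and Arm B is (334 − 10 − 10)/334 = 314/334. Arm A investigator ORR is (34 + 20)/334 = 54/334 and Arm B is (34 + 10 − 10)/334 = 34/334.

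In cases 1 and 2 the concordance difference is exactly zero while the investigator odds ratio is far from the BICR odds ratio of 1.00. The zero does not depend on the assumed counts; it follows whenever U + D is the same in both arms. In cases 3 and 4 total disagreement differs, and the concordance difference is −6.0 points (95% CI −8.5 to −3.5 and −10.3 to −1.7 respectively).

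**Sampling behaviour.** Simulation of 50,000 trials per scenario, 334 per arm, BICR ORR 10% in both arms. The two-sided 5% test on the concordance difference is added here for illustration; the SAP plans none.

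- 5% upgrades in Arm A, 2.5% up and 2.5% down in Arm B: concordance is 95% in both arms and the test rejects in about 5% of trials, as it does with no bias. Investigator ORR is 15% vs 10% and one-sided significant at 0.025 in about 50%.
- 2.5% up and 2.5% down in both arms, plus 5% extra upgrades in Arm A: concordance is 90% vs 95% and the test rejects in about 70%.

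**Which directional measure.** An obvious candidate is net upgrade, (U − D)/N, which equals investigator ORR minus BICR ORR. Suppose both arms have the same reader error: upgrade probability u among BICR non-responders and downgrade probability d among BICR responders. Net upgrade at BICR response rate p is u(1 − p) − dp, so the expected A-minus-B difference is −(u + d)(p_A − p_B). Without any bias, this is non-zero whenever response rates differ. With assumed u = 3% and d = 30%:

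- No bias, p = 2% vs 10%: −0.33 × (−0.08) = +2.6 points. The 95% CI lies above zero, a false signal, in about 36% of trials.
- Real bias, u doubled to 6% in Arm A, p = 20% vs 5%: (0.06 × 0.80 − 0.30 × 0.20) − (0.03 × 0.95 − 0.30 × 0.05) = −0.0120 − 0.0135 = −2.6 points, the wrong sign. The CI lies above zero in about 0.1%.

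The upgrade rate conditional on BICR non-response does not depend on p. Its CI lies above zero in between 2% and 3% of trials in the no-bias case and in about 41% in the real-bias case.

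**Conditional rates applied to case 1.** Upgrades: 20/300 = 6.7% vs 10/300 = 3.3%, difference +3.3 points (Wald 95% CI −0.1 to +6.8). Downgrades: 0/34 = 0% vs 10/34 = 29.4%, difference −29.4 points (−44.7 to −14.1; a rough interval, given the zero cell and 34 responders). Both point towards Arm A, which concordance cannot show.

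**The case against.** The strongest reply is that the check is neither useless nor the reader's only source. Four parts of it stand.

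- The miss needs similar total disagreement in both arms. With an equal background and extra upgrades in Arm A, concordance does fall. A reader might infer that the check cannot detect upgrading in Arm A at all; cases 3 and 4 show otherwise.
- The direction is recoverable from planned output. SAP section 6.2.2 analyses tumor endpoints by both assessors, section 6.2.2.3 gives ORR by arm, and the Table 11 cells carry direction. A reader might infer that a shift would go unseen anywhere in the report. That is not so: 15% vs 10% by investigator would be reported alongside 10% vs 10% by BICR. The SAP does not, however, name that comparison as a bias check.
- The consequences are limited. Protocol section 9.3 has BICR serve the primary analyses of the radiological endpoints, and the SAP uses BICR for response subgroups. The criterion for a positive study rests on overall survival alone. No decision rule depends on the criticised sentence, which is worded as a suggestion.
- The response and disagreement rates used here are assumptions.

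None of this rescues the inference. The symmetry lies in the formulas and holds for any counts.

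**Conclusion.** The interpretive sentence is wrong as written: similar concordance does not support a conclusion of no bias favouring an arm. The gap is real where total disagreement is similar across arms. Under the assumed 10% BICR response and 5% disagreement, it hides a 5-point shift in the investigator ORR difference.

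The reach is modest. It affects one supportive check on investigator-assessed response. The documents do not support reading it as a threat to overall survival, to BICR-assessed response or to the trial's conclusion. Correction is still worthwhile, because the SAP already uses directional metrics for PFS and the counts needed are already planned.

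**What to change.** In SAP section 6.2.2.3:

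1. Delete the sentence on similar concordance, or qualify it to say that the rates measure the amount of disagreement and not its direction. Keep both rates as descriptive.
2. Add, per arm, the upgrade rate among BICR non-responders: (n13+n14+n15+n16+n23+n24+n25+n26) divided by all cells in BICR columns 3 to 6.
3. Add, per arm, the downgrade rate among BICR responders: (n31+n32+n41+n42+n51+n52+n61+n62) divided by all cells in BICR columns 1 and 2.
4. Report the between-arm difference in each with a 95% CI. State that a higher upgrade rate, a lower downgrade rate, or both, in Arm A may indicate bias in favour of avelumab. This parallels the use of EDR and LDR for PFS.
5. Net upgrade may be shown descriptively but should not be the bias criterion, because it differs between arms under identical reader error whenever true response rates differ.

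The cost is a wording change and two derived rates from counts already planned, with no new data. The downgrade rate will be imprecise if BICR responders are few, and should be read with its interval.

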6.2.2.4. Disease control

Disease Control (DC) is defined as BOR of CR, PR, non-CR/non-PD or SD. DC rate (DCR) is the proportion of patients with DC.

DCR will be summarized by frequency counts and percentages.

